### 3. Objectives, Endpoints, and Estimands

Objectives	Endpoints
Primary	
To demonstrate the efficacy of izokibep compared with placebo, as measured by percentage of subjects achieving HiSCR75  at Week 12	
 
HiSCR75a at Week 12
 

Secondary (Efficacy)	
To demonstrate that izokibep is efficacious compared with placebo as measured by:
 
 
Percentage of subjects achieving HiSCR90 at Week 12
 
Percentage of subjects achieving HiSCR100 at Week 12
 
Percentage of subjects achieving HiSCR50 at Week 12
 
Percentage of subjects who experience <math>\geq 1</math> disease flare through 12 weeks of treatmente
 
Change in Dermatology Life Quality Index (DLQI)
 
Percentage of subjects with baseline Hurley Stage II who achieve AN count of 0, 1, or 2 at Week 12
 
Percentage of subjects achieving at least 3-point reduction from baseline in NRS Patient Global Assessment of Skin Pain at its worst among subjects with baseline NRS <math>\geq 4</math>
 
HiSCR90b at Week 12
 
HiSCR100c at Week 12
 
HiSCR50d at Week 12
 
HS flares through Week 12
 
Change in DLQI from baseline to Week 12
 
AN count of 0, 1, or 2 at Week 12
 
Change from baseline in NRS Patient Global Assessment of Skin Pain at its worst at Week 12
 

Secondary (Other)	
To assess the safety and tolerability of izokibep as measured by the incidence of TEAEs, events of interest, SAEs, and clinically significant laboratory values and vital signs	
 
• TEAEs and SAEs
 
• Laboratory values and vital signs at collected timepoints
 

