#### **9.3.5. Safety Analyses**

Safety data will include summaries of exposure, AEs, SAEs, and laboratory data. No inferential statistics (p-values) will be reported for safety data.

Exposure will include the number of doses administered (including complete and incomplete doses) and reasons for missed or incomplete doses. Exposure will be reported through the planned collection at Week 12, Week 16, and for the entire study. For subjects assigned to receive placebo who later receive izokibep, exposure will further be summarized by placebo and izokibep.

Adverse events and SAEs reported before the first administration of study drug will be listed. All summaries will include only treatment-emergent events. The number of subjects who report 1 or more AEs, the number who report 1 or more severe AEs, the number who report 1 or more SAEs, and the number who report 1 or more AEs that leads to discontinuation of study drug will be summarized by treatment during the primary phase of the study and overall. Subjects who receive placebo during the primary phase will additionally be summarized by phase (placebo-controlled and after crossing over to active).

Laboratory data and vital signs will be summarized at each planned collection timepoint. Subjects with positive ADA results will be summarized by timepoint.

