2. INTRODUCTION

This study will be conducted to evaluate the efficacy and safety of izokibep in the treatment of subjects with moderate to severe Hidradenitis Suppurativa (HS). Izokibep is a small protein molecule that acts as a selective, potent inhibitor of Interleukin (IL) 17A, to which it binds with high affinity.

This study investigates izokibep in subjects with active HS, including tumor necrosis factor-alpha inhibitor (TNFi) naïve subjects, and those who had an inadequate response or intolerance to TNFi, or for whom TNFi is contraindicated. The study is intended to be 1 of 2 adequate and well-controlled studies to support a claim of efficacy of izokibep in subjects with HS. Hidradenitis suppurativa clinical response 75 (HiSCR75) at Week 12 will be utilized to compare izokibep to placebo, for the primary endpoint.

This statistical analysis plan (SAP) will define the final analyses planned for the study.

The study will be terminated early after all subjects completed (or discontinued) treatment at Week 32. A decision was made to write an abbreviated clinical study report (CSR). The analyses described thereafter reflect this decision.

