3.2 Secondary Objectives

Secondary objectives of this study are:

- To demonstrate that izokibep is efficacious compared with placebo as measured by:
 - Percentage of subjects achieving HiSCR90 at Week 12
 - Percentage of subjects achieving HiSCR100 at Week 12
 - Percentage of subjects achieving HiSCR50 at Week 12
 - Percentage of subjects who experience ≥ 1 disease flare through 12 weeks of treatment
 - Change in Dermatology Life Quality Index (DLQI)
 - Percentage of subjects with baseline Hurley Stage II who achieve abscess and inflammatory nodule (AN) count of 0, 1, or 2 at Week 12
 - Percentage of subjects achieving at least 3-point reduction from baseline in Numeric Rating Scale (NRS) Patient Global Assessment of Skin Pain at its worst among subjects with baseline NRS ≥ 4
- To assess the safety and tolerability of izokibep as measured by the incidence of treatment-emergent adverse events (TEAEs), events of interest, serious adverse events (SAEs), and clinically significant laboratory values and vital signs

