5. CHANGES IN THE ANALYSES SPECIFIED IN THE PROTOCOL

The secondary endpoint, "Percentage of subjects who experience ≥ 1 disease flare through 12 weeks of treatment" has been moved down the hierarchy of secondary endpoint testing to be the (last) seventh one in the order of testing.

The exploratory endpoint "Change of Modified Sartorius Score from baseline, Weeks 4, 8, 12, and 16" will not be analyzed due to inconsistent and unreliable data collection.

Due to the early termination of the study and the decision to write an abbreviated clinical study report, exploratory efficacy analyses will not be performed as written in the protocol. The efficacy endpoints for which analyses will be done as-written will be limited to the following:

- Primary:
 - HiSCR75 at Week 16
- Secondary/Exploratory:
 - HiSCR90 at Weeks 2, 4, 8, 16, and 32
 - HiSCR100 at Weeks 2, 4, 8, 16, and 32
 - HiSCR50 at Weeks 2, 4, 8, 16, and 32
 - AN count of 0, 1, or 2 at Weeks 4, 8, 16, 24, and 32
 - Change in NRS Patient Global Assessment of Skin Pain at its worst in subjects with baseline NRS ≥ 4 at Weeks 4, 8, 16, 24, and 32
 - HS flares through Weeks 4, 16 and 52
 - Change from baseline to Weeks 4, 8, 16, and 24 in DLQI

All remaining exploratory efficacy endpoint analyses will not be performed.

Limited safety summaries are planned for the purposes of abbreviated CSR. Clinical laboratory data, ECGs, vital signs, and physical exam results will not be summarized. These data will be provided as datasets.

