9.8.2 Adverse Events

The number and percentage of subjects with AEs as well as the number of events will be summarized by MedDRA-coded SOCs and PTs.

The following AE summaries occurring through Week 16 will be presented by treatment group and overall:

- Overall summary of TEAEs
- TEAEs by SOC and PT
- TEAEs by Cumulative Severity Category by SOC, and PT
- Related TEAEs by SOC and PT

- Related TEAEs by Cumulative Severity Category by SOC, and PT
- Serious TEAEs by SOC and PT
- Treatment-related Serious TEAEs by SOC and PT
- TEAEs of Special Interest by SOC and PT
- TEAEs leading to discontinuation by SOC and PT
- TEAEs Experienced by >= 5% Subjects in Izokibep Group by SOC and PT
- Summary of ISRs
 - Total Number of subjects having at least 1 ISR (including count of events)
 - Subjects and Event ISRs Count by severity in the following categories:
 - Grade 1 or above
 - Grade 2 or above
 - Grade 3 or above
 - Grade 4 or above
 - Summary of signs and symptoms (subject counts/percentages and count of events)
 - ISRs (Subjects) Count by Injection Visit (if 1 subject has an ISR corresponding to multiple visits, the subject is counted in both)

The AE summaries listed above will also be produced for Period 2 for subjects with at least one dose of study drug in Period 2 (SAFP2). These will also be presented for Period 1 + Period 2 (Total study) combined for the safety analysis set (SAF).

Within each summary, a subject will only be counted once within each SOC and PT.

Summaries by SOCs and PTs will be sorted by SOCs by descending order of total incidence and PTs within SOC by descending order of total incidence. Where PTs tie, PTs will be sorted alphabetically. Summaries by PTs only will be sorted by descending order of total incidence.

All AE data will be listed and AEs and TEAEs will be presented together. Treatment-emergence status as well as period will be indicated in the listing. The listing will present the relative start and stop day of the AE calculated relative to the first dose of treatment and will be presented for those subjects who received at least 1 dose of treatment. If the AE is “Ongoing” it will be indicated as such in the listing and the relative stop day will not be calculated. Only original dates will be presented in the listing even though the relative day may be based on an imputed date.

The following listings will be presented for the SAF:

- Listing of all AEs (flag will be included for TEAE and safety follow-up AE)

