9.8.3 Clinical Laboratory Assessments

Clinical lab data will not be summarized or listed for the purposes of abbreviated CSR.

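### The final safety outputs omit the laboratory (other than liver) and vital-sign part of the secondary objective, and the total-study adverse-event table sets crude percentages side by side over unequal izokibep time

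*SAP*

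**What the plan says.** **Objective and endpoint.** SAP 3.2 lists "clinically significant laboratory values and vital signs" within the secondary safety objective. The matching endpoint in Protocol 3 is "Laboratory values and vital signs at collected timepoints", and Protocol 9.3.5 commits to an output: "Laboratory data and vital signs will be summarized at each planned collection timepoint".

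**Planned outputs.** SAP 5 declares the change made for the abbreviated report: "Clinical laboratory data, ECGs, vital signs, and physical exam results will not be summarized". SAP 9.8.3 goes further: "Clinical lab data will not be summarized or listed for the purposes of abbreviated CSR". SAP 9.8.5 says the same of vital signs. Both are supplied as datasets only. SAP 9.8.3.1 keeps a table and listing for liver-injury criteria and Hy's Law.

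**Adverse events.** SAP 9.8.2 sets the measure: "The number and percentage of subjects with AEs as well as the number of events will be summarized by MedDRA-coded SOCs and PTs". It plans this in three views: through Week 16, Period 2 only, and both periods combined. No person-time rate is planned. The columns (SAP 8.1) are the placebo-then-izokibep sequence and izokibep throughout.

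**Early stop.** SAP 2 states: "The study will be terminated early after all subjects completed (or discontinued) treatment at Week 32".

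**The concern.** There are two separate gaps.

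1. Part of a stated objective has no dedicated output. Protocol 8.2.7 and 10.3.1 turn a laboratory or vital-sign finding into an adverse event only when the investigator considers it clinically significant, and abnormalities tied to the underlying disease are excluded unless worse than expected. Cytopenias are an event of special interest, but SAP 6.10.2.2 finds them by reviewing reported preferred terms, not laboratory values. A shift that no investigator reports is therefore invisible in the report. Protocol 2.3.1 says class risks will be monitored explicitly because few subjects have been treated so far.

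2. In the combined-period table, the placebo-first column mixes 16 weeks of placebo with later izokibep. For an event caused by the drug, that column will look safer than the izokibep column even when the on-drug risk is identical. No column gathers all izokibep time: the overall column of the combined table includes placebo time, and the overall column of the Period 2 table omits the izokibep group's first 16 weeks.

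**Working it through.** **Part 1: following one value through the outputs.** Take a post-baseline neutrophil, platelet, hemoglobin or creatinine value that crosses a threshold listed in Protocol 10.3.5.

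| Route to an output | Opens when |
|---|---|
| Laboratory table or listing (SAP 9.8.3) | never; none planned |
| Liver table and listing (SAP 9.8.3.1) | liver criteria only |
| TEAE tables and AE listing (SAP 9.8.2) | the investigator reports an adverse event |
| Special-interest table (SAP 6.10.2.2) | a reported preferred term is selected in the manual review |

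If no adverse event is reported, every route is closed. Vital signs follow the same path. The data needed already exist: SAP 6.10.3 derives change from baseline and low/normal/high categories, and SAP 6.10.5 derives vital-sign changes.

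**Part 2: exposure.** The SAP's own dose counts (6.10.1) come first. Weekly dosing at Weeks 0–15 gives 16 doses, at Weeks 0–51 gives 52, and at Weeks 16–51 gives 36. All three match the SAP.

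The early stop can be read as every subject ending at Week 32, or as the study closing when the last subject gets there, with earlier enrollees going on as far as Week 52. The SAP keeps Week 52 windows and outputs, so both ends are shown. Planned izokibep weeks, izokibep group versus placebo-first group:

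| Table | All stop at Week 32 | Full schedule |
|---|---|---|
| Through Week 16 | 16 on izokibep vs 16 on placebo | same |
| Period 2 | 16 vs 16 | 36 vs 36 |
| Total study | 32 vs 16 (ratio 2.0) | 52 vs 36 (ratio 1.44) |

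With 125 per group and no dropout (125 × weeks × 7 / 365.25), total-study izokibep time is 76.7 versus 38.3 person-years, or 124.6 versus 86.2.

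**Effect on a crude percentage.** Assume an event that occurs only on izokibep, at a constant 10 per 100 subject-years. This rate is an illustration; the documents give none. The proportion with an event is 1 − exp(−0.10 × weeks/52):

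- 16 weeks: 3.0%
- 32 weeks: 6.0%
- 36 weeks: 6.7%
- 52 weeks: 9.5%

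The total-study table would show 6.0% versus 3.0% (2.0-fold) or 9.5% versus 6.7% (1.4-fold), although the on-drug rate is the same in both groups.

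**The case against.** The strongest reply is that the objective concerns clinically significant findings, and the protocol requires those to be recorded as adverse events. They then enter the TEAE tables, and a finding that stops treatment enters the discontinuation table. The Protocol 10.3.5 values are only examples of what could lead to discontinuation. The reduction is declared and explained, the data are supplied, and liver tests are kept. This stands in part. It makes adverse-event reporting a partial substitute, but not detection independent of the investigator, which by-visit summaries would have given. An analysis outside this document may have tabulated laboratory data, since SAP 4.1 limits this SAP to the final analysis; the documents do not say. It could not have covered Period 2 in full, because SAP 8.6 notes that even Week 16 data were incomplete at the primary analysis.

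On exposure, the reply is largely right outside one table. Planned follow-up is equal through Week 16, and concurrent 1:1 randomization balances Period 2 apart from differential dropout. Even in the total-study table, total follow-up is equal; only the mix of drug and placebo differs. If an event occurred at the same rate on placebo, the two columns would agree. SAP 9.8.1 also summarizes doses and duration, so a reader could approximate an event rate, though not a subject-level incidence rate. The protocol plans no safety p-values and did not promise exposure-adjusted rates.

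**Conclusion.** The point holds in two limited parts.

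- **Main part.** The laboratory (other than liver) and vital-sign component of the secondary safety objective has no planned post-baseline table or listing in the final analysis. Findings that investigators do not report as adverse events will go unreported. This rests on the text alone.
- **Lesser part.** The total-study adverse-event table can show about a 1.4- to 2.0-fold gap for drug-caused events at an equal on-drug rate. This assumes a constant hazard, no such events on placebo, no dropout, and izokibep time equal to the planned schedule, ignoring the four-week window after the last dose.

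A reader might infer three stronger things that the documents do not support.

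- That the safety objective as a whole cannot be answered: TEAEs, SAEs and events of special interest are fully tabulated against placebo through Week 16.
- That all the adverse-event tables suffer from unequal exposure: only the combined table does.
- That the distortion reaches threefold: this needs 16 weeks (3.0%) set against 52 weeks (9.5%), a pairing that occurs in no planned table.

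**What to change.** 1. Add one table per period giving the number of subjects who cross each Protocol 10.3.5 laboratory threshold, with the worst shift in the SAP's existing low/normal/high categories, for neutrophils, platelets, hemoglobin and creatinine. The thresholds serve here only as reporting cut-offs.
2. Add one table of vital-sign change from baseline, using the SAP 6.10.5 derivation.
3. For SAEs, events of special interest and adverse events leading to discontinuation, add exposure-adjusted incidence per 100 subject-years in an any-izokibep column. Start the izokibep group at its first dose and placebo-first subjects at their first Period 2 dose. State how person-time is censored, consistently with the treatment-emergent window.
4. If items 1 and 2 are not adopted, amend SAP 3.2 to say that the laboratory (other than liver) and vital-sign component will not be assessed beyond reported adverse events.

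The cost is a few tables programmed from existing analysis datasets and a slightly longer abbreviated report. No new data are needed.

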6. STUDY ENDPOINTS

6.1 Schedule of Assessments

The assessments planned for each visit are presented in the Protocol in Table 1, Schedule of Activities (SoA).

6.2 Timepoint Definitions

6.2.1 Relative Day

All assessment days will be relative to the date of randomization. The date on which the subject is randomized will be considered as relative Day 1, while the day before that will be relative Day -1. There is no relative Day 0. Relative days will be calculated using the following formula only if the date of the assessment is fully known (i.e., the relative day will be missing if the assessment date is a partial date):

Relative Day =

- Date of Assessment – Date of Randomization+1 when Date of Assessment \geq Date of Randomization.
- Date of Assessment – Date of Randomization when Date of Assessment $<$ Date of Randomization.

The date of randomization for each subject will be taken from the Disposition eCRF page. The date of the last dose of study treatment for each subject will be taken from the Study Drug Administration form, with the last study drug administration date as the latest date of study drug regardless of the visit.

6.2.2 Visit and Timepoint Windows

In general, data will be analyzed using the nominal study visits as defined in the SoA in the protocol and reported on the eCRF.

If a subject discontinues the study early, the subject will have an early termination visit which includes efficacy and safety assessments. If the early termination visit occurs in a timeframe that corresponds to a scheduled efficacy or safety assessment (week 2, 4, 8, 12, 16, 20, 24, 32, or 52), and if the subject does not have an actual visit at or after the corresponding scheduled efficacy or safety assessment, the day ranges below will be used to map the early termination visit to a scheduled efficacy assessment for use in all efficacy summaries at that timepoint.

In addition, unscheduled visit results will not be included in analyses, unless the unscheduled visit corresponds to a nominal visit for which the result is missing or if the unscheduled visit is selected as baseline. If the nominal visit result is missing, then the unscheduled visit result will also be mapped according to the ranges in Table 1 and Table 2 below for efficacy and safety assessments, respectively. If multiple unscheduled visits fall into 1 analysis window, then the one closest to the scheduled day will be used for analysis. If the 2 unscheduled visits are equidistant from the scheduled day, the later assessment will be used.

Table 1: Visit Windowing for Efficacy Assessments

Nominal Visit	Scheduled Day	Analysis Window (Relative Days)
Day 1/Week 0 (Baseline)	1	[1, 1]
Week 2	14	[2, 21]
Week 4	28	[22, 42]
Week 8	56	[43, 70]
Week 12	84	[71, 98]
Week 16	112	[99, 140]
Week 24	168	[141, 196]
Week 32	224	[197, 294]
Week 52	364	[295, later]

Table 2: Visit Windowing for Safety Assessments:

Nominal Visit	Scheduled Day	Analysis Window (Relative Days)
Day 1/Week 0 (Baseline)	1	[1, 1]
Week 2	14	[2, 21]
Week 4	28	[22, 42]
Week 8	56	[43, 70]
Week 12	84	[71, 98]
Week 16	112	[99, 126]
Week 20	140	[127, 154]
Week 24	168	[155, 196]
Week 32	224	[197, 294]
Week 52	364	[295, later]

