e The 'Baseline/Screening' version of the C-SSRS will be conducted during the screening visit and the 'Since Last Visit' version of the C-SSRS will be completed at all other timepoints.

f Serious AEs will be recorded from the signing of informed consent through the 8-week follow-up visit (ie, 8 weeks after the last dose of study drug); AEs will be recorded from Day 1 (ie, administration of study drug) until 4 weeks after the last dose of study drug.

g Confirm ongoing antiseptic wash requirement at every visit. From screening through Week 16, subjects will complete a daily diary of their analgesic use. For Week 17 through Week 52 subjects will be required to tell site staff if they took any analgesics within 24 hours of their site visit. Subjects will refrain from taking analgesics 12 hours before the site visit, if possible.

h Lesion count must address all relevant anatomical regions in each subject. The AN count is the sum of abscesses and inflammatory nodules. Any unscheduled visit for disease worsening based on the investigator judgment will include AN count and will be recorded in the appropriate CRF.

i From screening through Week 16, subjects will complete a daily diary of their skin pain at home. For Week 17 through Week 32 and Week 52 visits, subjects will complete a single skin pain assessment at the site. Note: Subject may not be randomized if pain diaries are not completed for  $\geq$  3 out of 7 days (at a minimum) prior to the Day 1 visit.

j For subjects who consent to the optional photography substudy at selected sites, photographs will be taken.

k IGRA TB test (QuantiFERON recommended) will be performed. Note: See [Table 8-2](#) for guidance for handling various TB test results.

l Serum pregnancy test required for screening and urine pregnancy test required at all other visits for WOCBP. Local authorities may require more frequent pregnancy testing.

m Fecal calprotectin at screening only required if subject has a) prolonged or recurrent diarrhea b) prolonged or recurrent abdominal pain or c) blood in stool.

n Administration of study drug should be done last after all study procedures unless indicated otherwise.

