## 8. Study Assessments and Procedures

- Informed consent must be obtained before any study-related procedures are performed. In regions where the legal age of consent is older than 18 years, informed consent must be obtained from and signed by the subject.
- Study procedures and their timing are summarized in the SoA ([Section 1.3](#)). Protocol waivers or exemptions are not allowed.
- Day 1 corresponds to the date of the first dose of study drug.
- Visit/dosing windows of  $\pm$  3 days on either side of the scheduled visits/dosing are permitted; however, the investigator should try to keep the subjects on the original visit/dosing schedule. The window of  $\pm$  3 days is relative to Day 1 and applicable for all subsequent visits/dosing. The time between doses should be no less than 4 days and no more than 13 days.
- All assessments are to be completed before study drug administration, unless otherwise specified. It is recommended that patient-reported outcome assessments be completed first.
- Immediate safety concerns should be discussed with the sponsor immediately upon occurrence or awareness to determine if the subject should continue or discontinue study drug.
- Adherence to the study design requirements, including those specified in the SoA, is essential and required for study conduct.
- All screening evaluations must be completed and reviewed to confirm that potential subjects meet all eligibility criteria. The investigator will maintain a screening log to record details of all subjects screened and to confirm eligibility or record reasons for screening failure, as applicable.
- Procedures conducted as part of the subject's routine clinical management (eg, x-rays) and obtained before signing of the ICF may be utilized for screening or baseline purposes provided the procedures met the protocol-specified criteria and were performed within the timeframe defined in the SoA.
- Repeat or unscheduled samples may be taken for safety reasons or for technical issues with the samples.

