4. STUDY DESIGN

4.1 General Design

This is a Phase 3, pivotal, confirmatory, 1:1 randomized, double-blind, placebo-controlled, parallel group study to evaluate the efficacy and safety of izokibep in subjects with moderate to severe HS. Subjects must have HS lesions present in ≥ 2 distinct anatomic areas, 1 of which must be Hurley Stage II or Hurley Stage III, and a total AN count (total sum of abscesses and inflammatory nodules) of ≥ 5 . Subjects with draining fistula count of > 20 at screening or Day 1 will be excluded.

Overall, 250 subjects (125 subjects per treatment group) with moderate to severe HS are planned to be enrolled at sites globally in North America, Europe, and Asia Pacific. Additional sites and regions may be added.

Subjects meeting eligibility criteria will be randomized into 1 of 2 treatment groups in a 1:1 ratio as follows:

- Group 1 (n = 125): placebo every week (QW) from Day 1 through Week 15, then izokibep 160 mg QW from Weeks 16 to 51.
- Group 2 (n = 125): izokibep 160 mg QW from Day 1 through Week 51.

[figure not shown]
The first dose of study drug (i.e., izokibep or placebo) will be administered on Day 1.

Randomization will be stratified by prior TNFi use for HS (Yes/No) and Hurley Stage (II or III). Subjects enrolled with stable concomitant antibiotic use (dosing regimen has been stable for ≥ 4 weeks prior to first dose of study drug) will be capped at approximately 30%.

The maximum planned length of participation in the study for an individual subject is up to 63 weeks, which includes the following:

- Screening Period of up to 28 days (4 weeks)
- Treatment Period of 51 weeks
- Follow-up visit at 8 weeks after the last dose of study drug.

Figure 1: Study Design Schema

EOS = end of study; EOT = end of treatment; QW = every week

^aRandomization will be stratified by any prior TNFi use for hidradenitis suppurativa (Yes/No) and Hurley Stage (II or III).

^bSubjects in Group 1 (placebo QW) will receive placebo QW until Week 15, then izokibep QW beginning at Week 16 until Week 51. Subjects in Group 2 (izokibep QW) will receive izokibep QW.

^cAn 'end of treatment visit' will be conducted at Week 52 (± 5 days). A 'safety follow-up visit' will be conducted at Week 59 (± 5 days). For subjects who early terminate, the end of treatment visit should be completed 1 week after the last dose of study drug and safety follow-up visit completed 8 weeks after the last dose of study drug (± 5 days), where possible.

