6.2.5 Treatment Period

Data collected on Day 1 will be assigned to the Treatment Period unless the time (HH:MM) of data collection and time (HH:MM) of randomization are both recorded, and the data collection time is before the time of randomization. In this case, the assessment will be assigned to the Screening Period.

If the time (HH:MM) of data collection is not recorded but the protocol and/or CRF includes an instruction to the effect that all Day 1 assessments are to be performed prior to randomization, the data collected at Day 1 will be assigned to the Screening Period. However, adverse events and concomitant

medications starting on Day 1, will be assigned to the Treatment Period, unless the time (HH:MM) demonstrates otherwise. Adverse events occurring within 4 weeks of the last dose of study drug will also be assigned to the Treatment Period. Adverse events occurring > 4 weeks after the last dose of study drug will be assigned to the “Safety Follow-up Period”.

The Treatment Period will be defined as the time from the date/time of randomization to 1 week after the last dose or when the subject completes their End of Treatment visit. Adverse events that occur within 4 weeks of the last dose of study drug will be attributed to the Treatment Period as well.

Treatment Period will also be divided into 2 periods, Period 1 and Period 2:

- Period 1 is the placebo-controlled period, and will start at the date of randomization and end at Week 16 when Week 16 assessments are completed and before administration of study drug in Period 2 (at or after Week 16 dose date/time). If a subject discontinues study drug prior to Week 16 and continues to attend visits without treatment through Week 16 (e.g. eCRF visit or analysis visit Week 8, Week 12, Week 16), then these visits’ results will be considered in Period 1, and should be included in efficacy/safety summaries.
- Period 2 will start at the time of first administration of study drug at or after Week 16 and end at Week 56 or early termination/end of treatment visit. If a subject discontinued study drug prior to Week 16 and continues to attend visits without treatment after Week 16 (e.g. eCRF visit or analysis visit Week 20, 24, etc.), then these visits’ results will be considered in Period 2 and should be included in efficacy/safety summaries.

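### An unscheduled lesion count taken after the placebo group has switched to izokibep can be mapped to Week 16 and analysed as a placebo result

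*SAP*

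**What the plan says.** SAP 6.2.2 starts from nominal visits: "In general, data will be analyzed using the nominal study visits as defined in the SoA in the protocol and reported on the eCRF". Unscheduled visits are a fallback: "unscheduled visit results will not be included in analyses, unless the unscheduled visit corresponds to a nominal visit for which the result is missing", or the visit is chosen as baseline. When the nominal result is missing, "then the unscheduled visit result will also be mapped according to the ranges in Table 1 and Table 2 below". The Week 16 range is Days 99 to 140 in Table 1 (efficacy) and Days 99 to 126 in Table 2 (safety). The SAP puts Week 16 on scheduled Day 112 in both.

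Group 1 receives placebo through Week 15, "then izokibep 160 mg QW from Weeks 16 to 51" (SAP 4.1). SAP 6.2.5 makes Period 1 the placebo-controlled period, which is to "end at Week 16 when Week 16 assessments are completed and before administration of study drug in Period 2"; Period 2 begins with that administration.

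Unscheduled visits can carry the data needed for HiSCR. Protocol 1.3, footnote h, states: "Any unscheduled visit for disease worsening based on the investigator judgment will include AN count".

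Day windows for summaries are an SAP addition. Protocol 9.3.1 says they will not be used, and SAP section 5 does not list them as a change.

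**The concern.** The mapping rule depends on calendar day and on the nominal result being missing. It does not look at what the subject was taking. For the placebo arm, most of the Week 16 range lies after the switch to izokibep. A lesion count taken there is Period 2 data under 6.2.5 and a Week 16 result under 6.2.2, and the SAP does not say which rule prevails.

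Week 16 is the last timepoint of the placebo-controlled period, and SAP 9.7 compares the arms there on HiSCR50/75/90/100 and on AN count 0, 1 or 2. A count taken on izokibep does not belong in the placebo column.

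The imputation adds a second route. SAP 9.5 imputes missing values in both arms from placebo-group data only. The example code selects that group by planned arm and models Week 16. A mapped on-izokibep count from a placebo-randomised subject would therefore help define the placebo reference used to fill in Week 16 for both arms.

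**Working it through.** **Inputs.** Week 16 scheduled Day 112 and ranges 99-140 and 99-126 (SAP 6.2.2, Tables 1 and 2); switch of Group 1 at Week 16 (SAP 4.1); relative day = date minus randomization date plus 1 (SAP 6.2.1); a ±3-day tolerance that "is relative to Day 1 and applicable for all subsequent visits/dosing" (Protocol 8); 125 planned per arm (SAP 4.4).

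**Reproducing the limit.** The upper limits are midpoints between adjacent scheduled days.

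- Table 1, which has no Week 20 row: (112 + 168)/2 = 140.
- Table 2, which has one: (112 + 140)/2 = 126.
- Week 12 in both tables: (84 + 112)/2 = 98.

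Day 140 thus comes from visit spacing, with no allowance for the switch.

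**How far the range runs past the switch.** On schedule the Week 16 dose falls 112 days after Day 1, which is relative Day 113. Table 1's range has 140 − 99 + 1 = 42 days.

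- Counting from Day 113: 140 − 113 = 27 days (27/42 = 64%).
- Counting from the SAP's Day 112: 140 − 112 = 28 days (28/42 = 67%).
- With ±3 days around either anchor (Days 109 to 116): 140 − 116 = 24 to 140 − 109 = 31 days.
- On weekly dosing this allows 4 to 5 izokibep doses by Day 140.
- Table 2 runs 126 − 113 = 13 days past the switch (14 from Day 112).

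**A case that follows the rules literally.** A placebo subject misses the Week 16 visit, takes the first izokibep dose at Week 17, and has an unscheduled lesion count on Day 130. SAP 6.10.1 itself provides for a missed Week 16 dose with later dosing. The nominal Week 16 result is missing and Day 130 lies in 99-140, so the count becomes the subject's Week 16 result in the placebo column.

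**Size.** The documents do not give the number of such subjects, so k below is an assumption. The direct shift in the unweighted placebo HiSCR rate is at most k/125. The last column shows the shift if the substituted result changed the response probability by 20 points, the design difference at Week 12 (35% − 15%).

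| k | Largest shift (points) | Shift at a 20-point difference (points) |
|---|---|---|
| 1 | 0.8 | 0.16 |
| 3 | 2.4 | 0.48 |
| 5 | 4.0 | 0.8 |
| 10 | 8.0 | 1.6 |

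The AN count 0-2 analysis uses only baseline Hurley Stage II subjects. Its denominator is smaller and is not stated, so one subject weighs more there. The effect through the imputation model is not in the table.

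**After a pre-dose condition.** For placebo subjects who switch, the days on which an on-izokibep count can be mapped to Week 16 fall to zero.

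**The case against.** The strongest reply is that this is a narrow fallback at a descriptive timepoint, and that the intended boundary is already written in 6.2.5. Much of that stands.

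- **Narrow route.** Three things must coincide: no nominal Week 16 count, izokibep already started, and an unscheduled count by Day 140. Scheduled Week 17 and Week 20 counts stay at their own visits. An early termination visit is mapped only "if the subject does not have an actual visit at or after the corresponding scheduled efficacy or safety assessment", so that route is nearly closed for anyone dosed at a Week 16 or later site visit.
- **No confirmatory role.** SAP 8.6 and 9.5 keep Week 16 outside the alpha-controlled sequence.
- **Not every late mapped visit is wrong.** Placebo subjects who stopped study drug but stayed in the study, or whose Week 16 dose was delayed beyond the visit, had taken no izokibep at that visit. Subjects given an antibiotic that could affect HS are set to non-response at later timepoints whatever the mapped count.

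What does not stand is that 6.2.5 settles the matter. It defines periods, 6.2.2 assigns visits, and neither refers to the other. A programmer following 6.2.2 would map the visit.

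A reader might go further in several ways that the documents do not support:

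- **DLQI, pain and flares.** Footnote h requires only an AN count at unscheduled visits for worsening. Pain through Week 16 is a 7-day diary average. Flare already counts unscheduled visits directly, without this substitution.
- **A known direction of bias.** Some unscheduled visits are made for worsening, but those at issue occur on izokibep, and not all need be for worsening.
- **64% as a risk.** It is a share of calendar days, not a probability of contamination.
- **The Table 1 and Table 2 limits as an error.** Their difference is only midpoint spacing. Table 2 matters little here, since laboratory, ECG and vital-sign data are not summarised and Period 1 adverse events are cut by dose date and time.

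**Conclusion.** The gap is real and small. Read literally, SAP 6.2.2 allows a lesion count taken on izokibep to be analysed as a placebo Week 16 result for HiSCR50/75/90/100 and AN count 0-2, and to enter the placebo-based imputation model for Week 16. It contradicts the end of Period 1 in 6.2.5.

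Each affected subject moves the placebo HiSCR rate directly by at most 0.8 points, assuming 125 placebo subjects in the denominator. The number affected is unknown and probably low, and the direction cannot be determined.

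It would be tempting to conclude that the primary result is compromised, particularly because SAP section 5 lists HiSCR75 at Week 16 under its primary heading. The documents do not support that. SAP 6.7, 8.6 and 9.5 place the primary endpoint at Week 12, whose range ends on Day 98, before the switch, so observed Week 12 results are not affected. One small indirect path remains: the example code for the first imputation step lists Week 16 together with Week 12, so a mapped Week 16 count could inform an intermittently missing Week 12 count.

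**What to change.** Add to SAP 6.2.2, for both tables: an assessment may be mapped to Week 16 only if it was made before the date and time of the subject's first Period 2 dose; otherwise Week 16 stays missing and is handled by the NRI and multiple-imputation rules of SAP 9.5. State a default for a visit on the dosing day with no recorded time. Protocol 8 places assessments before dosing, which supports treating such a visit as pre-dose.

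The ranges themselves can stay. Ending the range at Day 126 would not solve the problem, since 13 to 14 post-switch days would remain. It would also discard usable Day 127-140 results from subjects who took no Period 2 dose. Reassignment to Week 20 is not needed, and Table 1 has no such row.

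The cost is one sentence and one date comparison. The dose date and time are already needed to define Period 1 adverse events (SAP 6.10.2). The downside is that a few Week 16 values become missing and are imputed. SAP 8.6 describes the Week 12 analysis as already carried out, so the change should be recorded in the clinical study report, as Protocol 9.3.1 requires for changes made after unblinding. Reporting the number of subjects affected there would settle the size.
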